2.4 Secondary Endpoints

Efficacy endpoints

- The proportion of patients who achieve HBsAg loss who also have undetectable HBV DNA
- The proportion of patients in each group who become inactive HBV carriers; ie achieve a sustained virological response (HBV DNA < 2000 IU/mI & normal ALT values) at 3 years after randomisation
- Magnitude of reduction in quantitative HBsAg levels at 1, 6, 12, 24 & 36 months after randomisation
- Magnitude of changes in antiviral T cells response at 1, 5, 6, 12, 24 & 36 months after randomisation
- Magnitude of changes in NK cells response at 1, 5, 6, 12, 24 & 36 months after randomisation

Safety endpoints

• Proportion of patients in each group with exaggerated hepatitis flares

- Proportion of patients resuming nucleos(t)ide analogue therapy
- Adherence to pegylated interferon therapy

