2.1 Primary Objective

The primary objective is to determine the rate of HBsAg loss three years after randomisation in patients with HBeAg-negative chronic HBV infection. The rate of HBsAg loss will be compared in patients with simple treatment discontinuation against patients who are given a short course of pegylated interferon after nucleos(t)ide withdrawal.

Loss of HBsAg, the most important serological marker of HBV infection, is widely accepted (including by FDA & EMA) as an indication of cure in chronic HBV infection and is associated with absence of long term sequelae in non-cirrhotic patients. HBsAg is a cheap and universally available serum marker. Loss of HBsAg allows patients to be discharged from follow-up with consequent health-economic benefits.

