2.2 Secondary Objectives

- 1. To explore the safety of nucleoside withdrawal
- 2. To explore whether using interferon therapy in conjunction with treatment cessation is safe
- 3. To compare the number of patients in each treatment arm who become inactive HBV carriers.
- 4. Identification of virological and immunological biomarkers which predict a group of patients in which the loss of HBsAg is feasible
- 5. Correlate changes in HBsAg quantification and/or HBsAg status with innate and adaptive immune responses to HBV
- 6. To identify changes in immunological responses to HBV which occur after treatment withdrawal and after sequential NUC/IFN treatment

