2.3 Primary Endpoint

The primary endpoint will be the proportion of patients who lose HBsAg in each treatment arm 3 years after randomisation. Qualitative assays of HBsAg will be conducted on patients every 6 months using standard laboratory ELISA assays. Loss of HBsAg will be confirmed by repeating the test at least one month after the initial negative result. Patients in whom both tests are negative will be deemed to have lost HBsAg.

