8 STATISTICAL ANALYSES

8.1 Sample Size and power considerations

HBsAg loss is the primary endpoint; the trial will compare the rate of HBsAg loss in patients three years after cessation of nucleos(t)ide analogues with the rate of HBsAg loss in patients treated with pegylated interferon after cessation of nucleos(t)ide analogues. Only one published study provides an estimate of the rate of HBsAg loss in patients who stopped treatment after 4 years of nucleos(t)ide analogues which was 10% at 1 year,18% at 2 years and 24% at 3 years. A similar study reported by Berg (EASL 2015) confirmed the 10% HBsAg loss reported at 1 year. In the present study we will recruit some patients who have had treatment with nucleos(t)ide analogues for only 3 years and we will therefore use a conservative assumption for the rate of HBsAg loss in this group at 15% at 2 years and 20% at 3 years.

There is no data on the rate of HBsAg loss in patients who have been treated with nucleos(t)ide analogues and subsequently been treated with pegylated interferon. In a trial of pegylated interferon for naïve HBeAg negative hepatitis infection 42.4% had lost HBsAg at the end of follow up if the level of HBV DNA had been <70 IU/ml at the end of treatment. As this is an exploratory study we have assumed that the rate of HBsAg loss in this group will be 30% at 2 years and 40% at 3 years. This increment would represent the very significant clinical benefit which would justify the use of interferon (with associated side effects) in this group of patients.

A trial with 90% power to detect a difference in HBsAg loss between these groups (40% vs 20%) at the P < 0.05 threshold would require 109 subjects in each arm. Therefore allowing for ~10% withdrawal / dropout in each arm we will aim to recruit 120 subjects to each arm; a total of 240 patients in total. If either arm is discontinued after the pilot, then there will still be at least 80% power in comparison with an alternative trial arm in the post pilot participants.

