8.2 Data Analysis

(i) Primary Endpoint Analysis

This analysis will be performed primarily on an intention to treat (ITT) basis. The ITT population will be all subjects who have been randomized. Secondarily, a per protocol analysis will be performed. The per protocol population will be those confirmed to be eligible who have not resumed nucleos(t)ide analogues for patient/ physician preference and those, in the interferon arm, who have completed at least 8 weeks of interferon therapy. Rates of HBsAg loss will be compared between the two groups using logistic regression adjusting for the stratification factors HBsAg titre and centre. Results will be presented as odds ratios and their 95% confidence intervals.

(ii) Secondary outcomes

Secondary outcomes to be compared between the two groups will include the primary outcome assessed at one year and at two years from baseline. Kaplan-Meier plots will be produced to show the persistence of HBsAg. The plots will be supported by formal secondary analyses using Cox proportional hazards model methods

Achievement of the inactive carrier state (defined above) will be analysed using the same procedures as the primary outcome. A statistical analysis plan will be developed and approved by the Trial Steering committee prior to any regular analysis for reports to the Data Monitoring Committee. This plan will include details of the statistical methods to be used to analyse the outcomes, and describe the methods to undertake sensitivity analyses for handling missing data. The plan will contain conform with the Clinical Trials Unit standard operating procedures

(iii) Predictors of HBsAg Loss

Predictive factors for HBsAg loss will be explored using univariate and multivariate logistic regression analysis. Separate models will be fitted for the following variables: gender, age, duration of antiviral therapy, viral genotype, viral load pre-treatment, HBsAg titre, centre, peak ALT value post withdrawal, peak viral load post withdrawal, hepatic cccDNA, number of infected hepatocytes and ELISPOT counts. Odds ratios and their 95% confidence intervals produced from each of the models will be presented. Following this, a multivariate logistic regression analysis will be performed will include the variables that were statistically significant in the univariate analysis plus a variable for treatment group.

(iv) Safety analysis

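### The inactive-carrier endpoint is defined by HBV DNA and ALT alone, so it also counts patients who have lost HBsAg, and its difference between arms can come wholly from the primary outcome

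*Protocol*

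**What the plan says.** Secondary objective 3 (Protocol section 2.2) is "To compare the number of patients in each treatment arm who become inactive HBV carriers". Section 2.4 turns this into "The proportion of patients in each group who become inactive HBV carriers; ie achieve a sustained virological response", and the rule in brackets is "HBV DNA < 2000 IU/mI & normal ALT values) at 3 years after randomisation". Section 8.2(ii) refers back to that rule: "Achievement of the inactive carrier state (defined above) will be analysed using the same procedures as the primary outcome". Under section 8.2(i) those procedures are logistic regression, primarily in everyone randomised. Neither place requires persisting HBsAg or sets aside patients who have lost it.

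The primary endpoint is read at the same time point: "the proportion of patients who lose HBsAg in each treatment arm 3 years after randomisation" (section 2.3). Section 2.1 describes HBsAg loss "as an indication of cure in chronic HBV infection". The first efficacy endpoint in section 2.4 concerns patients with HBsAg loss who also have undetectable HBV DNA, so the protocol expects patients with loss who meet at least the DNA half of the carrier rule.

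**The concern.** The label and the rule describe different groups. By the protocol's own account, a patient who has cleared HBsAg is cured and is no longer a carrier. If HBV DNA is low and ALT normal, the rule still scores that patient as an inactive carrier. Three month-36 records show this:

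- HBsAg negative, DNA undetectable, ALT normal: counted, but cured.
- HBsAg positive, DNA 800 IU/ml, ALT normal: counted, as the label intends (leaving aside whether the patient is back on drug).
- HBsAg positive, DNA 50,000 IU/ml: not counted, as intended.

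Objective 3 asks how many patients in each arm become inactive carriers, and the rule does not answer that. If interferon raises HBsAg loss, the gain passes into this endpoint as well. A reader could then take one effect for two, or read a higher carrier rate on interferon when fewer patients are HBsAg-positive carriers.

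**Working it through.** **Inputs from the protocol.** Section 8.1 assumes for control a "rate of HBsAg loss in this group at 15% at 2 years and 20% at 3 years", and for interferon that "the rate of HBsAg loss in this group will be 30% at 2 years and 40% at 3 years". The target is 120 per arm.

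**The plan's own figure.** For 20% vs 40%, two-sided 5%, 90% power and pooled variance, n = [1.96 × √(2 × 0.3 × 0.7) + 1.282 × √(0.2 × 0.8 + 0.4 × 0.6)]² / 0.2² = (1.270 + 0.811)² / 0.04 ≈ 108.3, rounded up to 109 per arm, as stated. Then 109 × 1.10 ≈ 120. The planning rates are therefore read correctly here.

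**Assumptions, not in the protocol.** Every patient with HBsAg loss meets the DNA/ALT rule. The same proportion q of HBsAg-positive patients meets it in each arm, so interferon has no effect on the carrier state among those who stay positive. Dropout is ignored.

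**Formulas.** HBsAg loss occurs in 24 of 120 (control) and 48 of 120 (interferon).

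- Written rule: (24 + 96q)/120 vs (48 + 72q)/120, a difference of 0.2 × (1 − q).
- HBsAg-positive carriers: 96q/120 vs 72q/120, a difference of −0.2q.

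| q | Written rule, control vs interferon | Difference (points) | HBsAg-positive carriers | Difference (points) |
|---|---|---|---|---|
| 20% | 36% vs 52% | +16 | 16% vs 12% | −4 |
| 30% | 44% vs 58% | +14 | 24% vs 18% | −6 |
| 40% | 52% vs 64% | +12 | 32% vs 24% | −8 |
| 50% | 60% vs 70% | +10 | 40% vs 30% | −10 |

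The two differences have opposite signs throughout.

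**Relaxing the first assumption.** Let only 80% of patients with loss meet the rule, and let HBsAg-positive carriers be 30% vs 25% of the arm. The written rule gives 0.8 × 20 + 30 = 46% vs 0.8 × 40 + 25 = 57%, still in favour of interferon.

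**Where the reversal ends.** If all patients with loss meet the rule, the written endpoint favours interferon as long as the fall in HBsAg-positive carriers is smaller than the 20-point gain in loss. Carriers of 40% vs 20% would give 60% vs 60%.

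**Size of the overlap.** With arms pooled, patients with loss make up 0.6/(0.6 + 1.4q) of those counted: 68%, 59%, 52%, 46% and 42% for q of 20%, 30%, 40%, 50% and 60%.

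**Retreated patients.** Section 5 expects up to 45% to need retreatment, and section 6.5(i) keeps them in the study. The rule does not mention treatment at 3 years, so those suppressed on drug would count too. If 45% in each arm were retreated, suppressed and separate from those with loss, and nobody else qualified, patients with loss would be 20/65 = 31% of those counted in control, 40/85 = 47% on interferon and 60/150 = 40% pooled.

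**The case against.** Read as a response endpoint, the rule is sound. Section 2.4 equates the state with sustained virological response, and section 1 uses the same thresholds as the criterion of successful interferon therapy. A patient who clears HBsAg with low DNA and normal ALT has responded, and dropping the best outcomes would penalise the arm with more of them. On that reading 44% vs 58% is a correct result and only the label is loose. This stands, and it is why the fix keeps the two-state endpoint and does not exclude patients with loss. It does not remove the point, because objective 3 and section 8.2(ii) both call the state carriage.

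One may also say that the word carrier already implies HBsAg positivity and that an analysis plan would settle the detail. But the protocol writes out a definition and later points back to it, so the stated rule is the operative one.

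Three stronger readings are tempting and are not supported:

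- *The endpoint largely repeats the primary.* This depends on a carrier rate that the protocol does not give. The share of patients with loss drops below one half once q reaches 50%, and to 40% in the retreatment case above.
- *The arms are unequal by design.* The 20% and 40% are planning assumptions. If interferon does not change HBsAg loss, the overlap adds no difference.
- *The overlap yields a significant result.* An unadjusted two-proportion test at 120 per arm gives p of about 0.03 at q = 30%, but about 0.06 at 40% and 0.10 at 50%.

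**Conclusion.** The point holds as an overlap between label, rule and primary outcome. As written, the endpoint counts patients with HBsAg loss who meet the DNA/ALT rule, nothing in the protocol excludes them, and the difference between arms can come wholly from HBsAg loss. Under the planning rates and the stated assumptions, the written rule favours interferon by 16 to 10 points while HBsAg-positive carriers are 4 to 10 points fewer. These figures illustrate direction and size and do not predict the result: the carrier rate is assumed, and so is the 20-point gain in loss. The rule's silence on nucleos(t)ide use adds a second group whose presence blurs the meaning of the endpoint. This concerns one secondary endpoint. It should be corrected, but the primary analysis and the sample size stand.

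**What to change.** In sections 2.2, 2.4 and 8.2(ii), rename the two-state endpoint and keep its logistic regression. Two names are possible, and the choice should be explicit. *Sustained virological response* fits the rule as it stands. *HBsAg loss or inactive carrier state* also counts patients with loss who miss the DNA/ALT thresholds, so the rule would have to say so.

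Under either name, report by arm the exclusive states at 3 years:

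1. HBsAg loss as defined in section 2.3 (with the number also meeting the DNA/ALT rule).
2. HBsAg positive with HBV DNA below 2000 IU/ml and normal ALT, shown separately for patients on and off nucleos(t)ide analogues.
3. Neither.

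Objective 3 is then answered by the second state, read beside the first.

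A proportional-odds comparison of the three states is optional. At q = 30% the cumulative odds ratios are (0.40/0.60)/(0.20/0.80) = 2.67 for loss and (0.58/0.42)/(0.44/0.56) = 1.76 for loss or carrier, so the proportionality assumption could not be taken for granted.

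The cost is wording. HBsAg, HBV DNA and liver function tests, which include ALT (section 5.6), are already scheduled at week 156 in both arms (section 5.3). Section 6.5(i) already records the date of and reason for restarting nucleos(t)ide analogues, and concomitant medication is recorded at every visit.

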5 PROCEDURES AND MEASUREMENTS

The trial will be open label meaning that both patients and their medical staff will know to which arm of the trial they are randomised. All patients in the trial will discontinue nucleos(t)ide analogues at baseline with the exception of the interferon arm in the alternative protocol (see Figures 2 and 3).

Occurrence of flares which require recommencement of nucleos(t)ide analogues will be an important measure of safety and efficacy in this trial and will therefore not be counted as a withdrawal from the study. Based on the previous studies of treatment cessation it is reasonable to expect up to 45% of patients to require retreatment.

A. Control arm

Patients randomised to the control arm will discontinue their nucleos(t)ide analogue treatment at baseline. They will be followed up until 3 years after randomisation.

B. Interferon arm

Patients randomised to the Interferon arm will discontinue their nucleos(t)ide analogue treatment at randomisation. No treatment will be given for 4 weeks and then they will commence pegylated interferon 180 mcg s.c. o.w α 2a and will continue taking weekly interferon for a total of 16 weeks. They will subsequently discontinue all antiviral medications. They will be followed up until 3 years after randomisation.

Although pegylated interferon has a long list of side effects which may be both unpleasant for the patients and potentially harmful, poor adherence to treatment is not anticipated. All the centres in this study are experienced in the use of pegylated interferon for the treatment of both HBV and HCV infection and invariably achieve adherence rates over 95%.

Control and combined interferon treatment Protocol – see Figure 2

By the end of the pilot phase, if more than 40% of patients in the interferon arm experience exaggerated flares then the arm will be modified to a control and combined interferon treatment protocol in which pegylated interferon is added to the nucleos(t)ide analogue for 16 weeks from randomisation and prior to cessation of therapy rather than leaving a gap between nucleos(t)ide analogues withdrawal and pegylated interferon treatment (and compared to the control arm still). They will subsequently discontinue all antiviral medications after the 16 weeks. They will be followed up until 3 years after randomisation.

Interferon and combined interferon treatment Protocol – see Figure 3

NUC-B PROTOCOL Version 2.0 12 th Aug 2016	Sponsor Imperial College

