6.5 Discontinuation of Study Treatment and Withdrawal from Study

(i) Recommencement of nucleos(t)ide analogues

Retreatment with nucleos(t)ide analogue therapy will be recommenced according to the following criteria for exaggerated flares:

- 1. Disturbance of liver synthetic function
 - a. Bilirubin > 35 uMol/l
 - b. INR > 1.3
- 2. ALT > 20 x upper limit of normal
- 3. If HBV DNA and/or ALT remain persistently elevated for more than 6 months
- 4. If, in the opinion of investigator or patient there is a risk to health

It is possible that there may be variation in the criteria used to determine whether a patient with hepatitis flare post cessation would need to be restarted on treatment according to criteria number 4. Data will be collected on patients considered for retreatment to determine whether any systematic differences appear between the two groups.

Recommencement will not be considered as a withdrawal from the study. A form will be completed in the eCRF to document the date and reason for recommencement. Patients who resume nucleos(t)ide analogue therapy will be monitored at intervals at unscheduled visits until ALT, Bilirubin and INR test results begin to normalise and once they have returned to normal then the patients will return to the study visit schedule until the end of the study.

(ii) Permanent discontinuation of study treatment

Subjects may discontinue study medication for the following reasons:

- At the request of the subject.
- Adverse event/ Serious Adverse Event
- Allergic reaction to IMP
- In the event of pregnancy
- If the investigator considers that a subject's health will be compromised due to adverse events or concomitant illness that develops after entering the study.

(iii) Withdrawal from Study

Withdrawal from the study refers to discontinuation of study treatment and study procedures and can occur for the following reasons:

- Subject decision
- Loss to follow-up

In this situation the patient will be encouraged, where possible, to resume the nucleos(t)ide analogue treatment which they were taking before enrolling in the study.

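### The inactive-carrier endpoint has no off-drug condition, so patients controlled on restarted nucleos(t)ide analogues count as successes and the arm with more retreatment can look better

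*Protocol*

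**What the plan says.** Section 2.4 defines the endpoint as "The proportion of patients in each group who become inactive HBV carriers; ie achieve a sustained virological response", with the criteria "HBV DNA < 2000 IU/mI & normal ALT values) at 3 years after randomisation". It serves secondary objective 3 in section 2.2. Section 8.2 (ii) fixes the analysis: "Achievement of the inactive carrier state (defined above) will be analysed using the same procedures as the primary outcome". The primary outcome is analysed first by intention to treat, where "The ITT population will be all subjects who have been randomized".

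On retreatment, section 5 says that "it is reasonable to expect up to 45% of patients to require retreatment". Section 6.5 (i) adds: "Recommencement will not be considered as a withdrawal from the study". Retreated patients are seen at unscheduled visits until ALT, bilirubin and INR recover, and "once they have returned to normal then the patients will return to the study visit schedule until the end of the study".

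The secondary per-protocol analysis in section 8.2 (i) is limited, among other conditions, to patients "who have not resumed nucleos(t)ide analogues for patient/ physician preference". Resumption of therapy is also a safety endpoint of its own in section 2.4.

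**The concern.** An inactive carrier is someone who controls the virus without treatment. The Introduction (section 1) uses the same response term with the same two thresholds for a state measured 24 weeks after interferon has ended. Section 2 gives the overall aim as learning whether finite nucleos(t)ide treatment is feasible. A patient back on the drug has not achieved finite treatment, yet nothing in the section 2.4 definition stops that patient counting as a success.

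Retreated patients are also likely to qualify. Section 4.1 admits only patients whose HBV DNA was below 400 IU/ml for at least two years on this drug class, which is one fifth of the endpoint threshold. Section 6.5 (i) returns them to scheduled visits only after ALT has normalised. One of its restart criteria is persistently raised HBV DNA or ALT, so patients who fail the endpoint off drug are moved onto the drug that makes them pass it. That clinical rule is not in question here; the endpoint simply takes no account of it.

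At stake are the answer to secondary objective 3 and the meaning of the reported rate. Retreatment marks failure of the withdrawal strategy, but the endpoint rewards it.

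**Working it through.** **Figures in the plan.** The protocol gives no expected rate or power for this endpoint. Its only sample-size figure, 109 per arm for HBsAg loss of 40% against 20% at 90% power, reproduces exactly (two-sided 5%, no continuity correction) and is not affected by this point.

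**Inputs.**
- r: share of an arm back on nucleos(t)ide analogues at 3 years. The protocol gives up to 45% retreated overall (section 5) and no split by arm. Treating all of them as still on drug at month 36 is an assumption.
- s: share of those patients with HBV DNA below 2000 IU/ml and normal ALT. Assumed 95%, range 80–100%.
- q: share of non-retreated patients meeting the same criteria. Assumed 50%, range 30–50%.

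**Formulas.**
- Rate as written = (1 − r)q + rs
- Rate with an off-drug condition = (1 − r)q

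**Main illustration** (q = 50% in both arms, s = 95%):

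| | Control, r = 45% | Interferon, r = 30% | Interferon − control |
|---|---|---|---|
| Off-drug | 0.55 × 0.50 = 27.5% | 0.70 × 0.50 = 35.0% | +7.5 points |
| As written | 0.275 + 0.45 × 0.95 = 70.25% | 0.350 + 0.30 × 0.95 = 63.5% | −6.75 points |

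In the control arm, 0.45 × 0.95 = 42.75 points of the 70.25% are maintained by the drug, or 61% of the patients called inactive carriers. Over q = 30–50% and s = 80–100% at r = 45%, that share runs from 57% to 73%.

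**When the ranking reverses.** With equal q and s in both arms:
- As-written difference, high- minus low-retreatment arm = (r₁ − r₂)(s − q)
- Off-drug difference = −(r₁ − r₂)q

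The signs are opposite whenever s exceeds q. For retreatment of 45% against 25%, with q = 30–50% and s = 80–100%:
- As written: 0.20 × (0.30 to 0.70) = 6 to 14 points in favour of the arm with more retreatment.
- Off-drug: 0.20 × (0.30 to 0.50) = 6 to 10 points against it.

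**If interferon also helps non-retreated patients** (q = 60% against 50%, other inputs as in the main illustration):
- As written: 0.70 × 0.60 + 0.30 × 0.95 = 70.5% against 70.25%, a difference of 0.25 points.
- Off-drug: 0.70 × 0.60 = 42.0% against 27.5%, a difference of 14.5 points.

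There is no reversal, but the benefit is almost entirely hidden.

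**If retreatment is equal in the two arms**, with equal s, the difference in points is the same under both definitions. Each arm's rate is raised by rs, which is 42.75 points at r = 45% and s = 95%.

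**The case against.** The protocol never says in words that retreated patients are successes. Given the terms used and the off-treatment sense in the Introduction, an off-drug state may well have been intended, and a SAP could say so. Retreatment is not hidden: it is a separate endpoint, its date and reason are recorded, and the per-protocol analysis removes some of these patients. The reversal depends on assumed inputs. Section 6.5 does not say how long retreatment lasts, and a patient restarted shortly before month 36 may not yet have a normal ALT. Finally, this is a secondary endpoint; the trial is designed specifically around HBsAg loss, and that comparison is untouched.

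Part of this stands. The size and direction of the distortion cannot be fixed from the protocol, a reversal is one scenario among several, and the primary analysis is not threatened. The rest does not remove the problem:
- The definition is set in the protocol, and section 8.2 points back to it, so a SAP that follows it inherits the gap.
- If an off-drug state was intended, the operative wording does not deliver it.
- The per-protocol set drops resumption by preference only. Patients retreated on the bilirubin, INR, ALT or persistence criteria stay in.
- The separate resumption endpoint does not change who counts as an inactive carrier. From two marginal proportions a reader cannot work out how many carriers were on drug.

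**Conclusion.** The concern holds. The definition in section 2.4, the all-randomised analysis set and the rule that restarting is not withdrawal together make a patient re-suppressed on nucleos(t)ide analogues a success. That conflicts with the protocol's own off-treatment use of the term and with its finite-therapy aim.

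In the main illustration, a 7.5-point advantage for interferon becomes a 6.8-point disadvantage, and about 43 points of the control-arm rate are drug-maintained. This rests on assumed values for s, q and the retreatment split, and on retreated patients still being on drug at month 36. What does not depend on the split is the inflation: the reported rate exceeds the off-drug rate by rs in each arm. The effect on the comparison ranges from none, when retreatment is equal, to a reversal when it differs and s exceeds q in both arms. Because the section 2.4 definition itself is at fault, it should be corrected there before outcome data are compared by arm.

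**What to change.** Amend section 2.4 so that an inactive carrier is a patient with HBV DNA below 2000 IU/ml and normal ALT at month 36 who has taken no nucleos(t)ide analogue at month 36 or in the preceding 24 weeks. State in section 8.2 (ii) that patients on these drugs in that period count as failures in the intention-to-treat analysis, and report control on retreatment as a separate category by arm.

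The 24 weeks follow the interval in the Introduction. The length is a design choice: a patient retreated early who stopped again before the window could still succeed, so the protocol should say whether that is intended.

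The cost is small. The eCRF already holds the date and reason for restarting, and concomitant medications are recorded at every visit. The last two scheduled visits, weeks 130 and 156, are 26 weeks apart and so span the window. No new visit or sample is needed, and the primary endpoint and sample size do not change. The reported rate will be lower.
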